7.2 Handling of Missing Dates

To facilitate classification of AEs (TEAE or not) and medications (such as prior or concomitant medication, start date of subsequent anti-cancer therapy), the partial/missing dates will be imputed following the rules below, unless otherwise specified.

End date will be imputed first and start date will be imputed based on the imputed end date. If year of the date is missing, the date will be considered as totally missing and imputed accordingly.

Dates	Imputation Rule
Last dose date	• If the last dose date in Discontinuation of Investigational Product form is partially missing, it will be imputed as the earlier one of: the last date in that year/month; death date (if applicable).
	Note: The imputed last dose date will be used for safety data derivation (such as TEAE identification and period classification for other safety data) only, but not for the variables in Section 4.1 Extent of Exposure.

^b Weekly schedule from Cycle 1 Day 15 to Cycle 6 Day 15.

^c Every 6 weeks (2 cycles) relative to the first dose, x is odd number.

^d If there is not date-matched tumor assessment visit in CRF, the IRC visit will be mapped by increasing the number in sequence.

Drug Substance: DZD9008 Version Number: Final 2.0

Protocol Number: DZ2019E0001 (Part B) Version Date: 16 Nov 2023

Dates Imputation Rule AE end Date If end date is totally missing, then end date will be imputed as the earlier one of following dates: date of the last visit/contact (up to safety follow up) for the patient and death date (if applicable). If only day of end date is missing, end date will be imputed as the earlier one of following dates: the last day of that month, date of the last visit/contact (up to safety follow up) for the patient and death date (if applicable). If only month (or month and day) of end date is missing, end date will be imputed as the earlier one of following dates: the last day (Dec31) in that year, date of the last visit/contact (up to safety follow up) for the patient and death date (if applicable). If the end date imputed is earlier than the start date collected (if available), then the end date will be set as equal to the start date. AE start date If start date is totally missing and end date is also missing, no imputation will be performed. If start date is totally missing and end date is not missing, start date will be imputed as the earlier one of following dates: end date of AE and date of the first dose of study medication. If only day of start date is missing, and start date is in the same month same year of first study medication, start date will be imputed as earlier one of following non-missing dates: end date of AE and date of the first dose of study medication. If only day of start date is missing, and start date is not in the same month same year of first study medication, start date will be imputed as the first day in that month. If only month (or month and day) of start date is missing, and start date is in the same year of first study medication, start date will be imputed as earlier one of following non-missing dates: end date of AE and date of first dose of study medication. If only month (or month and day) of start date is missing, and start date is not in the same year of first study medication, start date will be imputed as the first day (Jan01) in that year. AE becoming Two step imputation serious date

- The date will be imputed following the rules for AE start date.
- Becoming serious date will be imputed as the later one of AE start date and the imputed date from first step,

Imputation Rule Dates AE grade change Two step imputation date The grade change date will be imputed following the rules for AE start Grade change date will be imputed as the later one of AE start date, the previous AE change date under the same event and the imputed date from first step. medication/therapy If ongoing is checked, no imputation will be performed. end date If ongoing is not checked and end date is totally missing, then end date will be imputed as the earlier one of following dates: date of the last visit/contact (up to safety follow up for general concomitant medication) and death date (if applicable). If only day of end date is missing, end date will be imputed as the earlier one of following dates: the last day of that month, date of the last visit/contact (up to safety follow up for general concomitant medication) and death date (if applicable). If only month (or month and day) of end date is missing, end date will be imputed as the earlier one of following dates: the last day (Dec31) in that year, date of the last visit/contact (up to safety follow up for general concomitant medication) and death date (if applicable). medication/therapy If start date is totally missing, no imputation will be performed. start date If only day of start date is missing, start date will be imputed as the first day in that month. If only month (or month and day) of start date is missing, start date will be imputed as the first day (Jan01) in that year.

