4.3.1 Concomitant treatment

Information about any treatment within 4 weeks prior to starting of DZD9008 and all concomitant treatments given during the study along with reasons for the treatment will be recorded in the Case Report Form (CRF). After permanent discontinuation of DZD9008 and 28 day follow up, only subsequent regimens of anti-cancer therapy will be recorded in CRF. If medically feasible, patients taking regular medication, with the exception of potent inhibitors and inducers of CYP3A4 (see Section 4.2 and Appendix H), should be maintained on it throught the study period.

All patients must avoid concomitant use of medications, herbal supplements and/or ingestions of food with known potent inducer/inhibitory effects on CYP3A activity whenever feasible. Traditional Chinese Medicine should be avoided. Such drugs must have been discontinued for 1 week (CYP3A4 inhibitors) or 2 weeks (CYP3A4 inducers) prior to first administration of DZD9008. Guidance on medications to avoid, medications that require close monitoring and on washout periods is given in Appendix H.

Patients must avoid live vaccines whist receiving study drug and up to 30 days after the last dose of study drug.

Patients may receive any medication that is clinically indicated for treatment of adverse events. All concomitant medications should be captured on the electronic CRF (eCRF).

Other anticancer agents, investigational agents and radiotherapy should not be given while the patient is receiving DZD9008. The patient may be allowed to take localized palliative radiotherapy only if it has been confirmed local lesion is not progressing, and/or after overall response has been evaluated as disease progression. This is to avoid interfering tumor assessment in the event of disease progression. Study drug interruption is not required in the case of local palliative radiotherapy for pain control (excluding chest and brain). For local

Date: July 24,2023

palliative radiotherapy to chest and brain, study drug should be interrupted during and up to 7 days post the palliative radiotherapy. Definitive radiotherapy and other anticancer therapy is not allowed.

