4.2.1 Primary Efficacy Endpoint

The primary efficacy endpoint is ORR according to RECIST 1.1 assessed by IRC, where confirmation of response is required.

ORR is defined as the percentage of patients who have best overall response (BOR) of Complete Response (CR) or Partial Response (PR) prior to any evidence of progression (as evaluated by IRC based on RECIST 1.1). Any CR or PR which occur after a further anticancer therapy is received will not be included in numerator of the ORR calculation, where further anticancer therapy (also called as new anticancer therapy) includes the systematic anticancer therapy or definitive radiothrapy received for the study indication after first dose of DZD9008.

In part B of study, RECIST assessments will be performed by IRC and investigator independently, from Cycle 3 Day 1 (\pm 7 days) and then every 6 weeks (\pm 7 days). A visit overall response of CR is defined when all Target Lesion (TL) and Non-Target Lesion (NTL) lesions present at baseline have disappeared (with the exception of lymph nodes which must have short axis < 10 mm to be considered non-pathological) and no new lesions have developed since baseline. A visit response of PR is defined when the sum of diameters of the TLs has decreased by 30% or more compared to baseline (with no evidence of progression) and the NTLs are at least stable with no evidence of new lesions. More details regarding RECIST assessment can be found in the appendix F of CSP.

BOR is defined as the best response recorded from first dose of DZD9008 until RECIST progression is documented for each patient. BOR represents the best response that a patient has had prior to any subsequent cancer therapy received, irrespective of whether or not patients discontinued treatment of DZD9008. There are 5 potential categories for BOR (from best to worst): CR, PR, Stable Disease (SD), Progressive Disease (PD) and Not Evaluable (NE). When SD is believed to be the best response, at least 35 days from first dose (6 weeks minus 7-day visit window) is required.

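### Partial start dates of subsequent anticancer therapy are imputed without reference to DZD9008 dosing, so a genuine confirmed response can drop out of the primary ORR

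*SAP*

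**What the plan says.** SAP 7.2 names the dates it covers, including "medications (such as prior or concomitant medication, start date of subsequent anti-cancer therapy". For a medication or therapy start it gives three rules:

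- Day missing: "If only day of start date is missing, start date will be imputed as the first day in that month".
- Month, or month and day, missing: if "only month (or month and day) of start date is missing, start date will be imputed as the first day (Jan01) in that year".
- Date totally missing: nothing is imputed.

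None of these refers to the first dose, the last dose or any scan.

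The date then acts on the primary endpoint. SAP 4.2.1 states that "BOR represents the best response that a patient has had prior to any subsequent cancer therapy received", and takes out of the ORR numerator any CR or PR after further anticancer therapy. It defines such therapy as systemic treatment or definitive radiotherapy for the study indication given after the first DZD9008 dose. The estimand in SAP 2.1.1 applies the same cut-off. The IRC's own BOR is not used directly because it ignores new therapy, so BOR is re-derived with this date. DCR rests on the same BOR, and best tumor change (SAP 4.2.2.4) has the same cut-off. PFS does not, because it keeps data after new therapy.

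Protocol 4.3.1 states: "Other anticancer agents, investigational agents and radiotherapy should not be given while the patient is receiving DZD9008".

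**The concern.** Taking the earliest possible date is a sensible way to sort medications into prior and concomitant. Here the same rule sets an efficacy cut-off. An imputed start can fall months before the last DZD9008 dose, during a period when the protocol says no other anticancer agent should be given. Scans taken on DZD9008 are then treated as scans on the next drug, and a confirmed responder can become a non-responder.

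The totally missing date works the other way. There is no cut-off, so a response that first appears on the next drug, before any documented progression, could be credited to DZD9008.

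At stake are individual responder classifications in the primary analysis, plus BOR, DCR and best tumor change, and the possibility that two programmers following the same SAP would obtain different ORRs.

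**Working it through.** **1. The case that follows from the text (hypothetical dates).** Scans are due at Cycle 3 Day 1, that is 42 days after first dose, and every 6 weeks after that.

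| Event | Date |
|---|---|
| First dose | 7 Nov 2022 |
| First PR (day 0 + 42) | 19 Dec 2022 |
| Confirming PR (day 0 + 84) | 30 Jan 2023 |
| Last DZD9008 dose | 1 Sep 2023 |
| Next therapy as recorded | 2023 only |
| Start imputed under SAP 7.2 | 1 Jan 2023 |

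The two PR scans are 42 days apart, so the 28-day confirmation rule is met. The imputed start falls between them. The confirming scan is excluded, and BOR goes from confirmed PR to SD (42 days exceeds the 35-day minimum for SD). Yet the patient took DZD9008 for another 243 days after the imputed start.

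**2. First dose and next therapy in the same year.** First dose 10 March, PR in April, confirmed in June, next therapy known by year only. The imputed start is 1 January, before first dose. If the CRF form identifies the therapy as subsequent, every response is erased. If the imputed date identifies it, the therapy is not further anticancer therapy under SAP 4.2.1 and is ignored. The SAP does not choose.

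**3. Day missing.** The start moves back within one month. A response is lost only if a scan needed for it falls in that same month.

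**4. Size, starting from the plan's design.** Inputs: stage 1 stops at 7 or fewer of 39 (Protocol 5.3.3); N=103 and expected ORR 0.30 (SAP 2.4); null ORR 0.17 (Protocol 7.9.7.1); one-sided 0.0125 (SAP 2.4). The 80% power appears only in the protocol's Version 8.0 change log and is taken as an assumption. The efficacy boundary c is redacted, so it is derived.

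P(reject | p) = Σ over x = 8 to 39 of Bin(x; 39, p) × P(X₂ ≥ c − x), with X₂ ~ Bin(64, p).

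| c | p = 0.17 | p = 0.30 |
|---|---|---|
| 26 | 0.0196 | 0.845 |
| 27 | 0.0111 | 0.801 |
| 28 | 0.0060 | 0.746 |

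The smallest c within 0.0125 is 27, with power 0.801, which agrees with the 80%. One responder is 1/103 = 0.97 points. At the boundary, 27/103 = 26.2% has tail probability 0.0111 and passes. With one erased, 26/103 = 25.2% has 0.0196 and fails.

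**5. Effect on power.** No frequency of partial dates is given, so the share of true responders erased is varied, with effective ORR = 0.30 × (1 − share) and c = 27.

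| Share erased | Effective ORR | Expected loss (103 × 0.30 × share) | Power |
|---|---|---|---|
| 0 | 0.300 | 0 | 0.801 |
| 1% | 0.297 | 0.31 | 0.784 |
| 2% | 0.294 | 0.62 | 0.765 |
| 3% | 0.291 | 0.93 | 0.745 |
| 5% | 0.285 | 1.55 | 0.702 |

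**The case against.** The strongest reply is that this will rarely happen. Protocol 6.3.6.3 collects subsequent treatment every 6 weeks. SAP 4.2.2.6 says 3-monthly survival contact, but either interval would normally identify the month. Protocol 5.3 requires anticancer treatment to be captured while tumor assessments continue, Appendix E provides for queries on missing data, and SAP 5.4.5 lists subsequent therapy by patient, so an implausible date could be seen. All of this stands. Against it, survival contacts may be with family or an outside physician, where partial dates can be expected, and a listing does not change a prespecified derivation.

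Direction also matters. Erasure counts against the drug, so as a conservative choice it is defensible in a test against a fixed null. That stands for erasure, but not for the totally missing date or the unsettled same-year case.

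Three stronger readings are tempting and are not supported:

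- A reader might infer that the same-year case certainly erases every response. Further therapy is limited to treatment after first dose, so the text allows the opposite result.
- A reader might infer that the AE rules in SAP 7.2 supply the floor that the therapy rule lacks. They say "start date will be imputed as earlier one of following non-missing dates: end date of AE and date of the first dose of study medication", which takes the earlier date and is no floor. When the year differs from that of first dosing, the AE rule also gives 1 January.
- A reader might infer that power falls to 0.746 or 0.679 (effective boundary 28 or 29). That assumes one or two losses with certainty. If 3% of therapies lacked the month, half the responders had switched by cut-off and half of those dates hit a needed scan (all assumptions), the expected loss is 30.9 × 0.03 × 0.5 × 0.5 = 0.23 patients and power is 0.788.

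**Conclusion.** The defect is real and narrow. A stated rule can turn a confirmed responder into a non-responder when the next therapy is known by year only and the confirming scan falls in that year after a first dose in an earlier year. The same-year case is undefined. The missing-day case needs a required scan in the month of the switch. A totally missing date leaves no cut-off.

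Erasure lowers ORR and does not inflate type I error. Each loss costs 0.97 points at n=103, and at the derived boundary a single loss reverses the decision. The formal test concerns the 300 mg arm, since SAP 5.6.1 treats the 200 mg p value as descriptive.

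This rests on 27/103 being the redacted boundary, on a frequency the documents do not give and that is probably low, and on no overriding rule existing in text not supplied (the SAP's numbering goes from section 7 to 9). The primary endpoint is directly affected and the correction is cheap, so it should be made before the analysis.

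**What to change.** Add to SAP 7.2, for efficacy derivations only:

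- Classify a therapy as subsequent from the CRF form on which it is recorded, not from the imputed date.
- Impute a partial start as the later of (a) the first day of the recorded month or year and (b) the day after the last DZD9008 dose, but never later than the last day of the recorded month or year, the therapy end date or death.
- If the start is totally missing, use the day after the last DZD9008 dose, with the same therapy-end and death caps.
- Impute a partial last-dose date by the existing rule for this purpose too. An extension is needed because the SAP now says "The imputed last dose date will be used for safety data derivation (such as TEAE identification and period classification for other safety data) only".
- For patients still on DZD9008, keep the first-of-period rule, floored at the day after first dose.

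List the affected patients and report ORR with and without the imputed cut-off as a sensitivity analysis. Leave the rule for general prior and concomitant medication unchanged.

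The cap at the end of the recorded period is essential. Without it, a therapy recorded as June with a last dose in September would be moved to September, overriding the record and crediting later scans to DZD9008.

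The cost is a short SAP paragraph, a small programming change and one listing. The downside is that a patient who started another agent while on DZD9008, with a partial date, may be dated late within the recorded period; the listing will show this.

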7.3 Tumor Assessment Date

[figure not shown]
The tumor assessment date in this section refer to image scan date rather than visit dates or image reading date.

The following rules will be applied:

- To calculate the date of progression, use the earliest of the dates of the assessment(s) within the corresponding RECIST visit;
- For patients censored for progression, use the latest date of the assessment from their last evaluable RECIST assessments;
- For determination of SD, use the earliest of the dates contributing towards a particular overall visit assessment;

- For the initial overall visit assessment which shows a response of CR/PR, use the latest of the dates contributing towards a particular overall visit assessment;
- For confirmation of CR/PR, use the earliest of the dates contributing towards the particular overall visit assessment of the subsequent CR/PR.

For the tumor assessment data evaluated by the investigators and collected in CRF, only the latest scan/clinical examination date of the TLs and NTLs will be recorded at each visit; for any new lesions detected, the earliest date will be recorded. The tumor assessment date by investigator will be derived based on the data available in CRF, following the rules above.

APPENDIX 10.

Appendix A Schedule of Event for part B of Study

Assessment	Screen	Cycle 1 (21 days)		Cycle 2 (21 days) onwards	Discontinuation	28-day follow up	Details in section of CSP	
Day	-28 to -1	1 h	8ª	15ª	1 ^b			
Informed consent	X							4.1.1
Demography & baseline characteristics	X							6.3.1
Medical/surgical history	X							6.3.1
Inclusion/exclusion criteria	X							4.1
Physical examination	X	X			X	X		6.3.2
ECOG performance status	X	X			X	X		6.3.2
Brain MRI or contrast enhanced CT	X							4.1
Pregnancy test (premenopausal females only)	Χ¢					X		6.3.4
Ophthalmology assessment i	X					X		6.3.5.4
Archival tumor tissue or fresh biopsy (mutation confirmation and/or companion diagnostics development) ^m	X							6.6.1

Drug Substance: DZD9008 Protocol Number: DZ2019E0001 (Part B)

Version Number: Final 2.0 Version Date: 16 Nov 2023

Assessment	Screen		(21 days)		Cycle 2 (21 days) onwards	Discontinuation	28-day follow up	Details in section of CSP
Day	-28 to -1	1 h	8ª	15ª	1 ^b			
Vital signs	X	X	X	X	X	X		6.3.3
Height	X							6.3.3
Weight	X	X			X	X		6.3.3
ECG	X	X##	X	X	X##	X		6.3.5
Clinical chemistry/ Hematology/Urinalysis	x	X	X	X	X	X		6.3.4
HBV/HCV/HIV/COVID-19 ^d	X							4.2
APTT/INR	X	X	X	X	X	X		6.3.4
Echocardiogram/MUGA e	X	←	On	Cycle 3 I	Day 1, then every 6 weel	√ √ √ √ √ √ √ √ √ √ √ √ √ √ √ √ √ √ √		6.3.5.2
Lung function test (LFT) e	X	←	O1	n Cycle 3	Day 1, then every 6 wee	ks→		6.3.5.3
EQ-5D-5L		X	Every 6 weeks relative to first dose X		X		6.9.1	
PRO-CTCAE and FACIT GP5 questions		X	Х	х	Weekly until the end of cycle 6, then on day 1 of each cycle	X		6.9.2 & 6.9.3

Drug Substance: DZD9008

Protocol Number: DZ2019E0001 (Part B)

Version Number: Final 2.0 Version Date: 16 Nov 2023

Assessment	Screen	Cycle 1 (21 days)		Cycle 2 (21 days) onwards	Discontinuation	28-day follow up	Details in section of CSP	
Day	-28 to -1	1 h	8ª	15ª	1 ^b			
PK blood samples ¹		X	X	X	X			6.5.1.3
Paired tumor biopsy (Subject joins PoM study only)	X				X (C2D1)			6.6.2.2
Plasma sample for the development of liquid biopsy companion diagnostic	X						6.6.1	
Blood sample for ctDNA & exploratory Biomarkers (optional)		X	X	X	X (C2D1-C6D1 and c	ontinuous every odd c	ycle D1 until disease	6.6.2.3
Blood sample for pharmacogenetics (optional)		X ^j						6.6.3
RECIST assessments ^f	X		←	О	n Cycle 3 Day 1, then ev	very 6 weeks		6.8.1
Dose with DZD9008			←	X	(daily dosing)			5.1.4
Concomitant medication		←						4.3.1
Adverse events g		←						
Survival status k		←			X		-	6.3.6.3

##: multiple time points for ECG.

^{*:} Day 1 of Cycle 2, 3, 4

Statistical Analysis Plan

Drug Substance: DZD9008

Version Number: Final 2.0 Version Date: 16 Nov 2023 Protocol Number: DZ2019E0001 (Part B)

 ± 1 -day visit window is allowed for C1D8 & D15.

- All study visits from Cycle 2 Day 1 onwards may be performed within a visit window of ± 2 days. Survival follow up may be performed within a visit window of ± 7
- Pregnancy test needs to be within 7 days of the first dosing. For Italy only: additional tests at pre-dose on Day 1 of Cycle 2 and each subsequent cycle, as clinically indicated, and during the safety follow-up period (2 weeks \pm 3 days after the last dosing).
- HBV/HCV/HIV/COVID-19 test can be done based on local practice.
- Echo/MUGA and LFT needs to be done within 14 days of the first dosing.
- It is suggested that site to conduct the first tumor assessment no earlier than C3D1 (±7days). CT is preferred for extracranial tumor. Same scan modality is required to use for tumor scan and RECIST assessment from baseline till follow up for one patient. Please refer to Appendix F of CSP about the details of RECIST assessment.
- AE will be collected from the first dosing of DZD9008 and SAE is required to be collected from inform consent
- For C1D1, -1 day window is allowed for laboratory safety testing and physical examination
- Eye examination includes: Visual acuity, Pupils, Intraocular pressure, External examination, Slit-lamp examination, and Fundoscopic examination (pupil dilate is not required) and others if clinically indicated.
- If for any reason the sample is not drawn prior to first dose (pre-dose at C1D1) it may be taken at any visit until the last study visit.
- Survival status including anti-cancer therapy will be collected every 6 weeks following disease progression or withdrawal from treatment.
- Multiple time point for PK sampling on C1D1 and C3D1. Hospitalization can be allowed for out of business time PK collection. If there is a dose interruption, dose reduction, or an early termination due to an AE, or there is an SAE, the investigator may choose to collect an unplanned blood sample (if possible) within the 24 hour after the last dose.
- m. Adequate amounts of archived tumor tissue or fresh biopsy (if archived tissue is not available) will be collected for Sponsor designated central laboratory confirmation of EGFR Exon20ins mutations. If a pre-study written documentation of EGFR Exon20ins in tumor tissue is available from Sponsor designated central laboratory using the designated assay, no additional tumor sample needs to be submitted. Requirements of tumor tissue sample collection can be referred to the Laboratory Manual.

Drug Substance: DZD9008

Version Number: Final 2.0 Protocol Number: DZ2019E0001 (Part B) Version Date: 16 Nov 2023

